### **Study Points of Reference**

#### **Baseline**

For any variable, baseline is the last assessment taken prior to or on the first investigational product administration unless stated otherwise; for subjects who did not receive any investigational product, baseline is the last assessment on or before the enrollment date.

#### **Study Day 1**

Study day 1 is defined as the first day of administration of the investigational product or the day of enrollment if the subject does not receive any investigational product. The day prior to Study Day 1 is considered as Day – 1.

#### **Study Day**

Study day is defined as the number of days from Study Day 1.

Post study day 1: study day= (date of interest – date of Study Day 1) + 1

Pre study day 1: study day= (date of interest – date of Study Day 1)

### **5.2 Study Dates**

#### **Informed Consent Date**

The date on which the subject signs the informed consent form.

#### **Last Dose Date**

The date on which a subject is administered the last dose of IP.

#### **Subject Level End-of-Study (EOS) Date**

End of study for each subject is defined as the date the subject last completed a protocol-specified procedure. The date will be recorded on the End of Study eCRF.

#### **Progressive Disease Visit**

Progressive disease visit should be performed any time during the study if the investigator suspects progressive disease and subject is experiencing worsening of cGVHD that requires the addition of new immunosuppressive medication(s) or an increase in systemic corticosteroid dose above baseline after week 4 of the study.

### **End of Treatment Visit**

Subjects discontinuing treatment prior to week 52 for any reason (see Section [8.1 in protocol](#)) will be asked to complete an End of Treatment visit within a window of  $\pm$  7 days of the next regularly scheduled visit after the last dose of efavaleukin alfa, consisting of all assessments included in the Week 52 visit. If the End of Treatment visit for a subject occurs  $<$  7 days after a progressive disease visit, then the procedures completed at the End of Treatment visit should only be those NOT performed at the progressive disease visit.

Subjects participating in the extended dosing, subjects discontinuing treatment prior to week 102 (Q2W dosing) or week 103 (QW dosing) will be asked to complete an End of Extended Treatment visit within a window of  $\pm$  7 days of the next regularly scheduled visit after the last dose of efavaleukin alfa, consisting of all assessments included in the Week 104 visit.

Subjects participating in the extended dosing, subjects discontinuing treatment after week 104 but prior to week 258 (Q2W dosing) or week 259 (QW dosing) will be asked to complete an End of Extended Treatment visit within a window of  $\pm$  7 days of the next regularly scheduled visit after the last dose of efavaleukin alfa, consisting of all assessments included in the Week 260 visit.

### **Safety Follow-up/End of Study Visit**

Upon completion of the treatment period or permanent discontinuation from the study treatment for any reason, a safety follow-up visit will be performed approximately 6 weeks ( $\pm$  3 days) after the last dose of efavaleukin alfa. Women of childbearing potential will be required to complete a pregnancy test at this visit.

### **Study Visit**

Since the actual visit for a subject may not exactly coincide with their scheduled visit date, the actual visit date is mapped to the analysis visit as per the analysis visit windows described in [Appendix G](#).

### **5.3 Subject Disposition**

#### **Exposed to IP**

Subjects are defined as exposed if they receive at least 1 dose of IP.

#### **Opted for extended dosing period**

---

Subjects are defined as opted for extended dosing period if subject has marked Yes for extended dosing on “**Extended Dosing Schedule**” eCRF.

### **Enrolled**

A subject is considered enrolled when the investigator decides that the subject has met all eligibility criteria and has been enrolled via the Interactive Voice Response

System/Interactive Web Response System (IVRS/IWRS). See protocol Section [6.4](#) for further details. The subject will be marked as enrolled on Enrollment eCRF and enrollment date will be included.

### **On-Study**

Subjects are considered on-study when they have enrolled but have not ended the study.

### **Planned Treatment Period**

**The time period from study day 1 until end of study or, for cohort 5 subjects, until the day before the first dose of IP at the reduced dose (█ mcg), whichever occurred first.**

### **Dose Reduction Period**

**For cohort 5 subjects, the time period from the first dose of IP at the reduced dose (█ mcg) until end of study, if applicable.**

### **Completed IP**

Subjects are defined as completing IP if the reason for ending IP on End of IP administration eCRF is marked as Completed. Based on whether subjects opted for extended dosing, these subjects will be stratified for summary purposes into those who 1) completed IP up to week 52 and did not opt for extended dosing, and 2) completed IP through extended dosing period.

### **Completed Study**

Subjects are defined as completing study if the reason for ending the study on EOS eCRF is marked as Completed. Based on whether subjects opted for extended dosing, these subjects will be further stratified for summary purposes into those who 1) completed the study up to week 52 and did not opt for extended dosing, and 2) completed the study through extended dosing period.

## **5.4 Arithmetic Calculations**

### **Change from baseline**

Change from baseline is the arithmetic difference between post-baseline and baseline. i.e. post-baseline minus baseline.

### **Percent change from baseline**

Percent change from baseline is the change from baseline divided by the baseline value times 100. If the change from baseline is not equal to 0 and the baseline value is 0 then percent change is not defined. If the change from baseline is equal to 0 and the baseline value is also 0 then percent change is 0.

### **Fold change from baseline**

Fold change from Baseline equals the post-Baseline value divided by the Baseline value. If the change from baseline is not equal to 0 and the baseline value is 0 then fold change is not defined. If the change from baseline is equal to 0 and the baseline value is also 0 then fold change is 1.

### **Dose Administered**

The dose administered ( $\mu\text{g}$ ) will be calculated as follows using quantity administered (mL), amount of IP used in preparation (mL) and total volume of preparation (mL) as reported in the clinical database and packaged drug concentration (mg/mL) as reported in manufacturing lot file:

- If dilution required,

Dose Administered = Quantity administered  $\times$  packaged drug concentration  $\times$  (amount of IP used / total volume of preparation)  $\times$  1000;

- If dilution not required,

Dose Administered = Quantity administered  $\times$  packaged drug concentration  $\times$  1000

If the dilution of IP is not required, the amount of IP used in the preparation of the dose and the total volume of preparation are not included in the calculation.

### **Number of days on IP**

Number of days on IP is defined as last dose date – first dose date + 1

### **Estimated glomerular filtration rate (eGFR)**

[figure not shown]
Estimated glomerular filtration rate at any visit will be calculated as follows using serum creatinine (umol/L) collected as part of chemistry labs at that visit and demographic information collected at screening:

For Japanese subjects:

$$\text{eGFR (mL/min/1.73 m}^2\text{)} = 194 \times [(\text{Creatinine}/88.4)^{-1.094}] \times (\text{Age}^{-0.287}) \times 0.739 \text{ (if female)}$$

For non-Japanese subjects:

$$\text{eGFR (mL/min/1.73 m}^2\text{)} = 175 \times [(\text{Creatinine}/88.4)^{-1.154}] \times (\text{Age}^{-0.203}) \times 1.212 \text{ (if black)} \times 0.742 \text{ (if female)}$$

## **5.5 Definitions**

### **AUClast**

Area under the concentration-time curve from time 0 (time of investigational product administration) to the time of the last quantifiable concentration.

### **AUCtau**

Area under the concentration-time curve after the first and last doses.

### **Cmax**

Maximum observed serum concentration.

### **Dose Limiting Toxicity (DLT)**

The DLT evaluation period for each subject is 4 weeks from the first dose of efavaleukin alfa. To be evaluable for a DLT, subjects must have received at least 2 doses of efavaleukin alfa, or have experienced a DLT within the DLT evaluation period. All subjects who experience a DLT will discontinue study therapy and complete safety follow up. Dose limiting toxicity events will be used to guide dose escalation decisions and to determine the maximum tolerated dose as described in Section [3.1](#).

These events will be marked as DLT on Events eCRF.

[figure not shown]
The following DLT criteria apply to the study:

[figure not shown]
- Non-hematological toxicity  $\geq$  grade 4 related to efavaleukin alfa. Non-hematological laboratory abnormalities without clinical significance will not be considered DLTs (based upon the investigator's discretion in conjunction with Amgen).
- Hematological toxicity  $\geq$  grade 4 related to efavaleukin alfa defined as decrease in peripheral counts (ANC or platelets) persisting longer than 72 hours, as measured by 2 separate results, that are not related to malignant disease relapse, infection, or other etiologies.
- Constitutional events (i.e., fever, fatigue)  $\geq$  grade 3 that are classified as serious adverse events by the investigator and related to efavaleukin alfa.
- Infection: Infection is considered an expected complication of cGVHD and its treatment. cGVHD itself increases the risk of infection, including life threatening infection. Therefore only grade 4 or 5 infections considered by the investigator to be related to efavaleukin alfa will be reviewed by the DLRM to determine whether the infection is considered a DLT.

[figure not shown]
Subjects who develop an uncontrolled grade 4 life threatening infection (e.g., sepsis, ARDS), as assessed by the investigator, will discontinue efavaleukin alfa and remain in the study for safety follow-up (see Section 5.4) after completing the 4-week DLT evaluation period, subjects will be evaluated by standard safety reporting.

[figure not shown]
2014 cGVHD NIH response Consensus criteria algorithm (NIH Form A - 2014)

All subjects in the study will have their clinical response assessed using the NIH cGVHD Response assessment (NIH Form A) as per the 2014 cGVHD NIH Consensus Criteria. Subjects will undergo repeat detailed assessment of ocular, oral, cutaneous, musculoskeletal, gastrointestinal, hepatic, and pulmonary systems per [REDACTED]

### **Treatment Emergent AE (TEAE)**

A treatment emergent adverse event is any adverse event categorized as adverse events starting on or after first dose of investigational product as determined by "Did event start before first dose of investigational product" equal to "No" or missing on the Events eCRF and up to and including 42 days after the last dose of investigational product excluding events reported after End of Study date on eCRF form, whichever is earlier.

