9.2.3.1.1 Time Period and Frequency for Collecting and Reporting Safety Event Information

9.2.3.1.1.1 Disease-related Events

Disease-related events are defined in [Appendix 4](#).

The investigator is responsible for ensuring that all disease-related events observed by the investigator or reported by the subject that occur after the first dose of investigational product through the safety follow-up visit/end of study are recorded using the Event CRF.

All serious disease-related events will be recorded and reported to the sponsor or designee within 24 hours. The investigator will submit any updated serious disease-related event data to the sponsor within 24 hours of it being available.

Disease-related events assessed by the investigator to be more severe than expected and/or related to the investigational product(s)/study treatment/protocol-required therapies, and determined to be serious, must be reported on the Event CRF as serious adverse events and recorded and reported per Section [9.2.3.1.1.3](#) and [Appendix 4](#).

Disease-related events pre-defined for this study are listed in [Appendix 11](#).

9.2.3.1.1.2 Adverse Events

The adverse event grading scale to be used for this study will be the CTCAE version 4.03 and is described in [Appendix 4](#).

The investigator is responsible for ensuring that all adverse events observed by the investigator or reported by the subject that occur from first dose of investigational product through the safety follow-up visit/EOS are reported using the Event CRF.

9.2.3.1.1.3 Serious Adverse Events

The investigator is responsible for ensuring that all serious adverse events observed by the investigator or reported by the subject that occur after signing of the informed consent through safety follow-up visit/EOS are reported using the Event CRF.

All serious adverse events will be collected, recorded and reported to the sponsor or designee within 24 hours, as indicated in [Appendix 4](#). The investigator will submit any updated serious adverse event data to the sponsor within 24 hours of it being available.

The criteria for grade 4 in the CTCAE grading scale differs from the regulatory criteria for serious adverse events. It is left to the investigator's judgment to report these grade 4 abnormalities as serious adverse events.

9.2.3.1.1.4 Serious Adverse Events After the Protocol-required Reporting Period

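### Adverse events starting on days 43 to 45 after the last dose can be collected under the protocol yet fall outside the SAP's treatment-emergent window

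*SAP*

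**What the plan says.** - **Collection period.** Protocol 9.2.3.1.1.2 makes the investigator responsible for reporting adverse events that occur "from first dose of investigational product through the safety follow-up visit/EOS".
- **Timing of the last visit.** SAP 5.2 states that "a safety follow-up visit will be performed approximately 6 weeks" after the last dose, with a tolerance of 3 days either way. Protocol 9.1.5 gives the same timing.
- **End of study for a subject.** SAP 5.2: "End of study for each subject is defined as the date the subject last completed a protocol-specified procedure". For a subject who attends, this is normally the safety follow-up visit.
- **Treatment-emergent window.** SAP 5.5 covers "any adverse event categorized as adverse events starting on or after first dose of investigational product". The upper limit that it sets on the start of the event is "up to and including 42 days after the last dose of investigational product". A second cap, tied to End of Study, is worded as "excluding events reported after End of Study date on eCRF form, whichever is earlier".
- **Where the definition is used.** SAP 2.1 makes the incidence of treatment-related and treatment-emergent adverse events, and of serious events, one of two primary endpoints. SAP 5.5 defines a treatment-related event as a subset of the treatment-emergent ones, and SAP 9.6.2 tabulates serious events as serious treatment-emergent events.
- **Concomitant medication.** Protocol 7.8.2 collects it through safety follow-up. SAP 5.5 counts newly started medication only up to 42 days after the last dose.

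**The concern.** The visit has a tolerance of 3 days and the analysis window has none. A site can keep fully to the schedule, see the subject on day 44, and record an event that began on day 43 or 44. The protocol requires that event on the case report form, and it falls on or before the End of Study date. The day-42 limit still removes it. Because the treatment-related and serious tables inherit the definition, a serious event on day 44 that the investigator judged related would be absent from all three summaries.

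The SAP gives no reason for excluding these events, and no planned table is set aside for onsets after day 42. The summary of serious events on or after a COVID-19 infection (SAP 9.6.2) is not tied to day 42, but it covers only that subset. SAP 9.1 puts only critical subject-level listings into the study report.

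**Working it through.** **The plan's own figure.** SAP 3.2 and Protocol 10.1.1 give the chance of seeing at least one event with a true incidence of 5%. The formula is 1 − 0.95^n.

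- n = 40: 1 − 0.95^40 = 0.871 (stated 87%).
- n = 30: 1 − 0.95^30 = 0.785 (stated 79%).

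Both reproduce. The point here does not depend on them, and the fix does not change them.

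**The windows, in days after the last dose.**

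- Visit target: 6 × 7 = 42. Earliest compliant day: 42 − 3 = 39. Latest: 42 + 3 = 45.
- Treatment-emergent limit: the earlier of day 42 and End of Study.
- Visit on days 39 to 42: End of Study comes at or before the limit, so collection and analysis end together and nothing is lost.
- Visit on day 43, 44 or 45: collection runs 1, 2 or 3 days past the limit.

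So 3 of the 7 allowed visit days lie beyond the limit, and the largest gap for a compliant visit is 3 days.

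**Share of follow-up time.**

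- Of the post-dose period: 3/45 = 6.7%.
- Of a one-year subject's study time, with the last dose on day 351 (every 2 weeks) or day 358 (weekly) from Protocol Table 2-2: 3/(351 + 45) = 3/396 = 0.76%, or 3/(358 + 45) = 3/403 = 0.74%.

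**Illustrative number of subjects.** The documents give neither the distribution of visit days nor the event rate in those days, so both are assumed. Expected subjects with an uncounted onset = 30 × (share of visits on days 43 to 45) × (chance of a new onset in those days).

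- Low: 30 × 1/7 × 0.01 = 0.04.
- Middle: 30 × 3/7 × 0.05 = 0.64.
- High: 30 × 1 × 0.10 = 3.0.

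These are upper figures for the tables. The tables report subject incidence, so a count changes only if the subject has no earlier treatment-emergent event in the same category. When a count does change, cohorts are small: with 3 to 6 evaluable subjects per cohort (SAP 3.1), one subject is 1/6 = 17 to 1/3 = 33 percentage points for that term.

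**After the fix.** If the window ends at End of Study or day 45, whichever is earlier, the uncovered days for a compliant visit fall from at most 3 to 0.

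**The case against.** The strongest reply is that there is no contradiction. Protocol Appendix 4 leaves the definition of treatment-emergent events to the SAP, and a collection period may legitimately be longer than an analysis window. Forty-two days is the protocol's nominal 6-week follow-up, used also for contraception and pregnancy reporting, and the 3 days are only a scheduling tolerance. The analysis is descriptive, with no statistical hypothesis (SAP 2.2). Dose decisions rest on dose level review of all available safety data, not on the treatment-emergent flag. The excluded events stay in the database. All of this is correct and keeps the point minor. It does not explain why on-study events collected on schedule should be left out of the primary safety tables.

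Three stronger readings are tempting, and the documents do not support them.

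- **A reader might infer that any event first found at a visit on days 43 to 45 is dropped.** The definition works on start date, and Protocol Appendix 4 requires the onset date to be recorded. An event disclosed on day 45 that began by day 42 still counts.
- **A reader might infer that abnormal laboratory, ECG, vital-sign or examination findings at that visit are lost because they carry the visit date as onset.** No section says they are dated that way. Protocol 9.2.4 generally keeps laboratory abnormalities without clinical significance out of the adverse event record and, where applicable, records the clinical sequelae instead. Laboratory and vital-sign values also have their own summaries (SAP 9.6.3.1 and 9.6.4), and Appendix G keeps the safety follow-up as an analysis visit with no day-42 cut-off.
- **A reader might take 3 of 7, or 43%, as the share of events or of final visits affected.** It is a share of allowed visit days. It becomes a share of visits only if visits are spread evenly over the window, which the documents do not show, and it is never a share of events.

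**Conclusion.** The mismatch stands, as a minor point. Events with onset on days 43 to 45, in subjects whose compliant safety follow-up visit falls on those days, are collected but left out of the treatment-emergent, treatment-related and serious treatment-emergent summaries. New concomitant medication has the same gap. The primary endpoint on dose-limiting toxicities in the first 4 weeks is untouched.

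The 3-day maximum follows from the text alone, for visits within the allowed window. The number of events is unknown and probably very small: the illustration gives 0.04 to 3.0 subjects in 30, about 0.6 in the middle case, on assumed inputs. The case for changing the rule is that it makes the primary safety tables cover the protocol's own collection period at almost no cost. It does not rest on any expected change in the safety conclusions.

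**What to change.** In the SAP 5.5 definition of a treatment-emergent adverse event, end the window at the End of Study date or 45 days after the last dose, whichever is earlier, judged by the event's start date. Stating the start date also settles the present End of Study clause, which refers to when an event is reported while the rest of the definition refers to when it starts. The 45-day cap still bounds the window for subjects who stop treatment but remain on study (Protocol 8.1). Apply the same limit to concomitant medication in SAP 5.5.

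The cost is a small edit to two definitions, a minor programming change, and possibly slightly higher adverse event counts. If the sponsor prefers to keep day 42, the lesser alternative is a separate listing of collected events with onset after day 42.

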### **Treatment-related Treatment Emergent Adverse Event (TRAE)**

A treatment-related AE is any TEAE with the relationship flag on the Adverse Events eCRF indicating there is a reasonable possibility that the event may have been caused by investigational medicinal product. This assessment is performed by the study investigator. In the unlikely event that the relationship flag is missing and an event is TEAE, then it will be considered treatment-related and corresponding footnote will be included in the summary table.

### **Baseline medications**

**Baseline medication is defined as any medication with a start date on or before Study Day 1 and ongoing while on study.**

### **Prior and Concomitant medications**

Prior medication is defined as any medication with start date and end date prior to the first dose date of IP. Concomitant medication is defined as any medication with start date prior to the first dose date of IP but which continued to be taken after the first dose of IP or any medication with start date on or after the first dose date of IP and up to and including 42 days after the last dose date of IP.

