3.2.3 Risk Assessment

The most common adverse events experienced by subjects included mild (grade 1) painless erythema at or near the injection site, sometimes accompanied by pruritus, that was self-resolving. As of 22 September 2020, 2 serious hypersensitivity reactions to efavaleukin alfa have been reported. The 2 events (grade 2 and 3, respectively)

occurred within the first 24 hours after initial dose and resolved without sequelae with symptomatic treatment (ie, systemic corticosteroids). More detailed information about the safety risks of efavaleukin alfa may be found in the Investigator's Brochure.

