### **9.6.9            Exposure to Concomitant Medication**

Number and proportion of subjects receiving medications/therapies of interest will be summarized by preferred term or category as coded by the World Health Organization Drug (WHODRUG) dictionary.

**Number and proportion of subjects who experienced a systemic corticosteroid dose reduction from baseline in subjects who were on systemic corticosteroid at baseline will be summarized by treatment group through week 52.**

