**14. Appendices**

## Appendix A. Technical Detail and Supplemental Information Regarding Statistical Procedures and Programs

### Imputation Rules for Partial or Missing Start Dates

The reference date for the following rules is the date of first dose of IP.

Start Date		Stop Date						Missing	
		Complete: yyyymmdd		Partial: yyyymm		Partial: yyyy			
		< 1 st dose	≥ 1 st dose	< 1 st dose yyyym m	≥ 1 st dose yyyym m	< 1 st dose yyyy	≥ 1 st dose yyyy		
Partial: yyyymm	= 1 st dose yyyymm	2	1	n/a	1	n/a	1	1	
	≠ 1 st dose yyyymm		2	2	2	2	2	2	
Partial: yyyy	= 1 st dose yyyy	3	1	3	1	n/a	1	1	
	≠ 1 st dose yyyy		3		3	3	3	3	
Missing		4	1	4	1	4	1	1	

1=Impute the date of first dose;

2=Impute the first of the month;

3=Impute January 1 of the year;

4=Impute January 1 of the stop year;

Note: For subjects who were never treated (first dose date is missing), partial start dates will be set to the first day of the partial month or first day of year if month is also missing.

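### SAP 5.5 defines baseline medication by date alone, so a steroid course begun after the first injection on Day 1, or a later drug imputed to that date, is classed as baseline

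*SAP*

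**What the plan says.** SAP 5.5 gives the rule: "Baseline medication is defined as any medication with a start date on or before Study Day 1 and ongoing while on study". SAP 5.1 fixes the reference day: "Study day 1 is defined as the first day of administration of the investigational product". That is a calendar day, not a time. On-study status, in SAP 5.3, is equally broad: "Subjects are considered on-study when they have enrolled but have not ended the study".

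The paragraph of SAP 5.5 after the baseline rule makes concomitant, among others, "any medication with start date on or after the first dose date of IP", up to 42 days after the last dose.

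Two outputs rest on baseline steroid use. SAP 9.4.2 lists systemic corticosteroids under baseline immunosuppressant medication. SAP 9.6.9 counts, through week 52, subjects who "experienced a systemic corticosteroid dose reduction from baseline in subjects who were on systemic corticosteroid at baseline". The SAP's list of changes names the baseline-medication definition, the immunosuppressant item and the steroid-reduction summary together as additions.

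For incomplete medication start dates, Appendix A uses the rule "1=Impute the date of first dose" in several cells of its table.

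**The concern.** A baseline class should hold what the subject was taking before treatment began. This one also takes in drugs started on the dosing day after the injection, including a drug given because of the injection.

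The case is realistic. Protocol 3.2.3 reports two serious hypersensitivity reactions, grade 2 and grade 3, within 24 hours of the initial dose, both treated with systemic corticosteroids. The SAP handles the reaction itself correctly, because treatment-emergence uses an eCRF question on whether the event began before first dose. On Day 1 the reaction could thus be treatment-emergent while the steroid that treats it is baseline.

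At stake are the description of background immunosuppression and the proportion with steroid reduction, in cohorts of 3 to 6 subjects.

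**Working it through.** The plan states no figure for this point, so there is nothing to reproduce. The check applies the rules to test records and then sizes the effect of one misclassified subject.

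**Classification as written**

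| Systemic steroid record | Baseline (5.5) | Concomitant (5.5) |
|---|---|---|
| Started weeks before Day 1, continuing | yes | yes |
| Started Day 1 after the injection, stopped Day 5 | yes | yes |
| Started Day 2, stopped Day 5, dates complete | no | yes |

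The second row is the problem: a course started after dosing sits with genuine background use.

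**Imputed dates.** In the Appendix A table, code 1 applies when the start is (a) partial and in the first-dose month, (b) year only and in the first-dose year, or (c) missing, provided the stop is on or after first dose or is missing. A fully missing stop date is treated as ongoing. A steroid begun months after dosing but recorded by year only can therefore be given a Day 1 start and meet the baseline rule.

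**Effect of one misclassified subject.** Let m be the true baseline users in a group and x those who truly reduce. Both are assumed, since the documents give neither.

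- If stopping counts as a reduction, x/m becomes (x+1)/(m+1).
- If it does not, x/m becomes x/(m+1).

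| m | x | Correct | Stopping counts | Stopping does not count |
|---|---|---|---|---|
| 3 | 0 | 0/3 = 0% | 1/4 = 25% | 0/4 = 0% |
| 4 | 1 | 1/4 = 25% | 2/5 = 40% | 1/5 = 20% |
| 5 | 1 | 1/5 = 20% | 2/6 = 33.3% | 1/6 = 16.7% |
| 5 | 5 | 5/5 = 100% | 6/6 = 100% | 5/6 = 83.3% |

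A subject already on background steroid who gets a temporary Day 1 increase leaves the denominator unchanged. Whether that subject enters the numerator depends on the comparison dose.

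**How often.** Protocol 3.2.2.3 gives about 136 exposed subjects across the programme. Take 2/136 = 1.5% as an assumed rate of steroid-treated first-dose reactions.

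- At least one among 30 subjects (the planned escalation size): 1 − (1 − 2/136)^30 = 36%.
- The same if only half of the steroid starts fall on the Day 1 date: 1 − (1 − 1/136)^30 = 20%.
- At least one in a cohort of 6: 1 − (1 − 2/136)^6 = 8.5%.

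The expected number in 30 subjects is 30 × 2/136 = 0.44. The documents give no rate for incomplete start dates, so that route cannot be sized.

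**The case against.** The strongest reply is that only the classification is in the text and the rest is inferred. SAP 9.6.9 does not cite 5.5, does not define a dose reduction, and does not say whether stopping a short course is one. SAP 5.5 sets no dose. The general rule, "baseline is the last assessment taken prior to or on the first investigational product administration unless stated otherwise", would arguably fix the comparison dose at or before the injection. All of this stands. A reader might infer that the plan scores withdrawal of a reaction course as steroid sparing; the documents do not say so. The general rule does not cure the classification, though: it concerns assessments and gives way where something else is stated, as 5.5 does for medications.

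The requirement that the drug be ongoing while on study also narrows the case. A single dose given and finished on Day 1 is arguably outside it, and a fully dated Day 2 start is outside. A multi-day course begun on Day 1 is inside.

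Overlap between baseline and concomitant is not itself a fault, since every continuing background drug belongs to both classes.

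The two reactions are programme-wide figures, and the programme includes healthy volunteers and other diseases. The documents do not place either in this study or date the steroid to Day 1. Nor do they show that any dose group would be favoured.

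The body of Protocol 7.8.2.1 (corticosteroids) and parts of the SAP are not visible, so a steroid-dose rule there cannot be excluded.

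Finally, simply barring code-1 dates would do harm. A long-standing background steroid with a missing start date also receives code 1, and the present wording keeps it as baseline.

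**Conclusion.** The concern holds for classification. By its own words, SAP 5.5 admits to baseline a multi-day systemic steroid course begun after the first injection on Day 1. With Appendix A code 1, it also admits later drugs with missing or partial start dates. These records enter the 9.4.2 table and, on the natural reading, the 9.6.9 denominator.

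Inflation of the reduction proportion is conditional on stopping being counted as a reduction. If it is not, the extra subject leaves the proportion unchanged or lowers it. With 3 to 5 true users, the table's illustrations show shifts of about 13 to 25 percentage points upward, or about 3 to 17 downward, where the proportion changes at all. These are hypothetical counts, not estimates.

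Few subjects are likely to be affected. The summary is descriptive, the SAP plans no statistical hypothesis for phase 1b, and the primary safety endpoints are untouched. The point is worth correcting because the rule is explicit, the groups are small and the change is cheap.

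**What to change.** In SAP 5.5, define baseline medication as started before the first IP administration and ongoing at it.

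For recorded Day 1 starts, decide by indication or linked adverse event, and class a drug given for a post-dose event as concomitant only. Start time should not be the criterion, because Protocol 7.8.2 lists start date and indication among the collected items but no time.

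For starts imputed by code 1, keep baseline status only where the prior-therapy or screening record, or the indication, supports pre-dose use. Protocol 7.8.1 already calls for complete prior GVHD therapy history, so genuine background steroids need not be lost.

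In SAP 9.6.9, cite the 5.5 definition, state that reduction is measured from the systemic steroid dose in force before the first injection, and say whether stopping counts. Inclusion criterion 106 already requires that dose to have been stable for at least 2 weeks.

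The cost is SAP wording, one derivation rule and review of a few Day 1 or incomplete-date records, with no new data. The number on steroids at baseline, or the number with a reduction, may fall slightly.
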